# 8. DISCONTINUATION OF STUDY TREATMENT AND/OR WITHDRAWAL OF PARTICIPANTS FROM THE STUDY

# 8.1. Discontinuation of Study Treatment

A participant *must* permanently discontinue aducanumab for any of the following reasons:

- The participant develops any new acute or subacute hemorrhage.
- The participant develops any treatment-emergent incident of cerebral hemorrhage > 1 cm in diameter on T2\* sequence.
- The participant develops a radiographically severe ARIA-H (10 or more treatmentemergent microhemorrhage or more than 2 treatment-emergent superficial siderosis)
- The participant develops any radiographic type of ARIA- E or ARIA-H accompanied by serious symptoms (according to the definition of serious adverse events in Section 11.1.2).
- The participant develops a cortical infarct (defined as > 1.5 cm in diameter irrespective of anatomic location).
- The participant develops more than 1 > 1 lacunar infarct (defined as  $\leq 1.5$  cm in diameter).
- The participant withdraws consent to continue study treatment.
- The participant experiences a medical emergency that necessitates permanent discontinuation of study treatment or unblinding of the participant's treatment assignment.
- The participant experiences an AE that necessitates treatment discontinuation or requires continued treatment that meets exclusionary criteria.
- The participant experiences a severe infusion reaction.
- The participant initiates treatment of Alzheimer's disease with a commercially available disease-modifying drug.
- At the discretion of the Investigator for medical reasons, including treatment-emergent ARIA events.
- At the discretion of the Sponsor for safety or other reasons.
- At the discretion of the Investigator or Sponsor for noncompliance.
- The participant becomes pregnant; study treatment must be discontinued immediately, and pregnancy must be reported according to protocol instructions.

The primary reason for discontinuation of study treatment must be recorded in the participant's CRF.

Participants who discontinue treatment are encouraged to remain in the study, attend a safety FU Visit 18 weeks after the last dose of study treatment, and immediately continue protocol required tests and assessments at a subset of the clinic visits (see Table 3) until the end of the study per the Schedule of Activities or until the participant withdraws consent.

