# 8.3. Withdrawal of Participants From Study

Participants must be withdrawn from the study for any one of the following reasons:

- The participant withdraws consent for participation in the study.
- The participant enrolls into another interventional clinical study in which an investigational treatment or approved therapy for investigational use is administered.
- The participant is unwilling or unable to comply with the protocol.
- At the discretion of the Investigator or Sponsor.

Note: A participant who discontinues study treatment will not be automatically withdrawn from the study, regardless of the number of doses missed. The participant is to remain in the study, and continue with a FU Visit 18 weeks after the participant's last dose of study treatment, and protocol-required tests and assessments at a subset of the clinic visits (see Table 3) until the end of the study or until the participant withdraws consent.

The primary reason for the participant's withdrawal from the study must be recorded in the participant's CRF.

Participants who are withdrawn from the study after receiving ≥ 1 doses of study treatment should complete the ET Visit after the reason for withdrawal is identified. For such participants, efficacy assessments specified at the ET Visit are not required if the participant discontinues treatment within 3 months of the previous efficacy assessment visit, and no significant changes in cognitive status are suspected by the Investigator; the site should notify the Sponsor and Medical Monitor in such cases. Participants who are withdrawn from the study are also to return to the site for a FU Visit 18 weeks after receiving their last dose of study treatment.

Participants should undergo an ET visit unless withdrawal is due to death or withdrawal of consent.

Participants who withdraw from the study may be replaced if enrollment is still open.

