#### 12.2.2.4. Considerations for Efficacy Endpoint Analysis

In analyses performed on the FAS, participants will be analyzed based on the intent-to-treat principle according to their randomized treatment assignment regardless of treatment received. The primary estimand on the treatment effect of aducanumab is for the primary endpoint based on the continuous variable of change from baseline scores in CDR-SB. This analysis is conducted for an estimand with a treatment policy strategy to handle all ICEs, with the following attributes as outlined by ICH E9 (R1):

- Analysis set: all participants in the FAS
- Variable: the change from baseline scores in CDR-SB at Week 78 regardless of ICEs
- Analysis set level summary: LS mean difference from MMRM model in change from baseline between aducanumab dose and placebo
- ICEs and strategies for addressing ICEs: all observed data to be included regardless of ICEs

The ICEs include treatment discontinuation or a change in concomitant use of Alzheimer's disease symptomatic medication.

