2.2.6. Sample Size Considerations

The sample size was mainly based on results from the primary analysis of Study 221AD302. Results from the post-PV4 population (i.e., the 221AD302 and 221AD301 protocol amendment in which the high dose of aducanumab was increased from 6 mg/kg to 10 mg/kg) in pooled data from Studies 221AD302 and 221AD301 were also considered. A total sample size of 1512 participants was planned to have approximately 90% power to detect a mean difference of 0.48 in change from baseline CDR-SB at Week 78 between the 2 treatment groups. This power

²All participants enrolled in the study are to return to the study site at 12 weeks after the last dose of study treatment for Follow up/End of Study visit. The follow-up visit is important and is intended to monitor the participant after a washout period that is based on the drug's half-life. However, if a study participant with their healthcare provider decides to initiate a disease-modifying Alzheimer's treatment outside of the clinical trial prior to completing all mandated protocol study visits, then the participant should withdraw from the study as per protocol (Protocol Section 8.3, Withdrawal of Participants from Study). For these patients when they are withdrawn, no further study visits should be completed.

⁴Pregnancy testing will only be required for women of childbearing potential.

calculation was based on a 2-sided t-test assuming equal variance with a final significance level of 0.05, an SD of 2.33, a dropout rate through Week 78 of 27%, and a randomization ratio of 2:1. The assumed mean difference of 0.48 between the 2 treatment groups represented an approximately 24% reduction in the placebo mean change from baseline at Week 78 if the placebo mean change is estimated to be 2.

In the original study design per protocol, a blinded assessment of the pooled SD for the primary efficacy endpoint may be performed approximately 3 months prior to the completion of enrollment and the sample size may be increased as a result. The sample size could also be increased using internal and external clinical study results that become available after the start of this study. In addition, the sample size may be increased if the dropout rate through Week 78 is estimated to exceed 27%. The sample size will not be reduced based on this assessment.

Following the study early termination decision on 31 January 2024, the blinded assessment of the pooled SD will not be conducted.

3. Definitions

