5.7. Safety Endpoints

5.7.1. Adverse Events

Analysis Methods

AEs will be analyzed based on safety analysis set. All AEs will be analyzed based on the principle of treatment emergence. A treatment-emergent AE is defined as an AE that started or worsened after the start of the first dose of study treatment.

To define treatment emergence for AEs with missing start or stop date or time the following additional criteria will be used:

- If both the start and stop dates for a particular AE are missing, then that AE is considered treatment emergent;
- If the start date for a particular AE is missing and the stop date/time falls after the first dose date/time, then that AE is considered as treatment emergent;
- If the start date for a particular AE was the same as the first dose date, and the start time was missing, then that event is considered treatment emergent.

For AEs with a partial start date, the year/month of the event date will be compared to that of the first dosing date to determine whether the event is treatment emergent.

In general, AEs will be analyzed based on incidence proportion. The incidence proportion (%) is defined as the number of subjects with an event divided by the total number of subjects in the analysis population. In determining incidence proportion, both single occurrence and multiple

occurrences of events will be counted as one incidence in the numerator. In the remainder of this document and in table titles, incidence proportion may be referred to simply as "incidence".

Adverse events are coded using the MedDRA dictionary. This coding system provides more than five levels to classify AEs. In general, AEs will be presented by SOC and PT but other classifications may be used if warranted.

An overall summary of AEs will be provided by treatment group and by treatment group stratified by ApoE status. This will generally include the following numbers and percentages of subjects: with any AE, with any AE by maximum severity, with any related AE (related to study drug as assessed by the investigator), with SAE, with related SAE (related to study drug as assessed by the investigator), with AE leading to drug discontinuation, with AE leading to study withdrawal, and fatal events.

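### Adverse events and ARIA that arise after a participant switches to a commercial disease-modifying drug are counted under the study-treatment group, and no output separates them

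*SAP*

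**What the plan says.** **Switching and follow-up.** Protocol 8.1 lists this among the reasons for which study treatment must stop permanently: "The participant initiates treatment of Alzheimer's disease with a commercially available disease-modifying drug". The same section adds: "Participants who discontinue treatment are encouraged to remain in the study", on the reduced visit schedule of Protocol Table 3. Protocol 8.3 confirms: "A participant who discontinues study treatment will not be automatically withdrawn from the study, regardless of the number of doses missed". Its withdrawal reasons do not name the start of a commercial drug.

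**After termination.** SAP 2.2.5, Table 1 footnote 2, reports the rule in the letter of 16 February 2024. It applies "if a study participant with their healthcare provider decides to initiate a disease-modifying Alzheimer's treatment outside of the clinical trial" before the mandated visits are complete; "then the participant should withdraw from the study as per protocol (Protocol Section 8.3, Withdrawal of Participants from Study"), and no visits follow the withdrawal.

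**Counting of events.** SAP 5.7.1 says: "A treatment-emergent AE is defined as an AE that started or worsened after the start of the first dose of study treatment". SAP 3.3 gives the same open-ended rule. It also defines an on-treatment period that closes 28 days after the last dose, but SAP 5.7.1 to 5.7.1.7 do not use it. AE recording runs to the final clinic visit, including the follow-up visit (Protocol 11.3.1).

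**Grouping.** The Safety Analysis Set groups by actual treatment received (SAP 3.6), and SAP 3.2 defines study treatment as the blinded aducanumab or placebo given in this study. ARIA and hemorrhage > 1 cm use the Safety MRI Analysis Set, for which SAP 3.6 states no grouping rule. CDR-SB is summarised descriptively on the FAS by randomised arm (SAP 3.6, 5.6).

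**The concern.** With the efficacy objectives abandoned, the main remaining content of the report is the safety of aducanumab against placebo, and ARIA is its central event. Aducanumab was itself on the US market under accelerated approval (Protocol 3.1), so a placebo participant could take the test drug, or another drug with a disease-modifying claim, outside the study and still be followed. An ARIA event after that switch falls inside the treatment-emergent window and counts as a placebo event. In an aducanumab participant, an event due to a different product counts as an aducanumab event.

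No planned output picks these cases out. The SAP 5.5.1 listing of placebo participants who received active doses draws on study-drug administration records, so it would not show commercial use. SAP 5.5.2 breaks out only symptomatic Alzheimer's drugs at baseline.

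**Working it through.** The plan states no figure on this point, so there is none to reproduce. The check has three parts.

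**1. Does a switcher's later event reach the tables?**
- Before the letter, a switcher stops study drug (Protocol 8.1) and may stay on the Table 3 schedule (8.1, 8.3). AEs are recorded to the final visit (11.3.1), any onset after first dose is treatment-emergent (SAP 5.7.1), and the group is set by blinded study drug (SAP 3.2, 3.6). The event is counted under the original study-treatment group.
- After the letter, footnote 2 has the switcher withdraw with no further visits, so collection ends.
- Remaining overlap: SAP 2.2.5 item 4 and Table 1 footnote 3 send participants already on the Table 3 schedule to any outstanding ET and follow-up visits. Both visits include brain MRI (the ET scan may be omitted if one was done within 14 days). If earlier switchers are among them, those scans can detect ARIA from a commercial drug.

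**2. How long was the period under the protocol rule?**
First dose was on 27 July 2022 (SAP 9.1). On 31 January 2024 that participant was at Study Day 553 + 1 = 554, which is Week 79 because Week 78 is Day 547. On 16 February 2024 it was Day 570. The exposure window is therefore at most about 18 months, and shorter for later enrollees.

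**3. How large could the effect on placebo ARIA-E be?**
Inputs from Protocol 3.3: ARIA-E 35.2% at 10 mg/kg and 2.7% on placebo; 10.0% of the 10 mg/kg group had symptoms in the setting of ARIA. SAP 2.2.3 gives more than 1000 enrolled, so at 2:1 about 1000/3 = 333 on placebo. *Assumptions:* a fraction x of placebo participants switch and stay in follow-up, and a switcher has risk r of a recorded event.

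Placebo rate = 2.7% × (1 − x) + r × x. Added cases = (rate − 2.7%) × 333.

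| x (assumed) | r = 35.2% (full Phase 3 detection) | Added cases | r = 10.0% (mainly symptomatic cases found) | Added cases |
|---|---|---|---|---|
| 2% | 2.646 + 0.704 = 3.35% | 2.2 | 2.646 + 0.200 = 2.85% | 0.5 |
| 5% | 2.565 + 1.760 = 4.33% | 5.4 | 2.565 + 0.500 = 3.07% | 1.2 |
| 10% | 2.430 + 3.520 = 5.95% | 10.8 | 2.430 + 1.000 = 3.43% | 2.4 |

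The r = 35.2% column is an upper-end illustration. Table 3 schedules brain MRI only at Week 104 and ET, plus unscheduled ARIA visits, and nobody had reached Week 104 by termination. The 18-week follow-up visit adds one scan. Most ARIA-E is asymptomatic (Protocol 3.2.3.2), so fewer cases would be found than under Phase 3 monitoring. The r = 10.0% column is only a rough lower comparison, because that figure covers symptoms with any ARIA.

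The contrast with 35.2% is 32.5 points without switching and 35.2 − 5.95 = 29.25 points in the most extreme cell.

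For rare events the scale differs. One case in 333 is 0.3%, so a single misattributed death, serious ARIA or hemorrhage > 1 cm can change a placebo cell from none to one.

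**The case against.** **Grouping.** A reader might infer that AEs and ARIA are counted by randomised arm. The documents do not say so: AEs go by actual study treatment, and the rule for the Safety MRI Analysis Set is unstated. The misattribution arises because a commercial drug does not alter the study-treatment group.

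**Footnote 2.** It largely closes the gap from February 2024, and this stands. It does not reach back to earlier switches.

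**CDR-SB.** A reader might infer that post-switch values corrupt the one remaining efficacy table. The protocol's estimand keeps all observed data regardless of intercurrent events: "The ICEs include treatment discontinuation or a change in concomitant use of Alzheimer's disease symptomatic medication". A switch forces treatment discontinuation, so keeping later values follows the declared strategy. On the Table 3 schedule, post-switch CDR could fall only around Weeks 50 and 78. CDR was later removed from the ET and follow-up visits, and the table is untested. A flag is the most that can be asked.

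**Existing visibility.** Concomitant medications are listed, CNS immunotherapy is disallowed (Protocol 7.7.1.2), and use of a disallowed therapy is a major deviation (SAP 9.2). A careful reader could trace a switch, but neither output separates the events in the tables.

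**A cut at the switch.** The open-ended definition matches Protocol 12.5.3, and footnote 2 ties the follow-up visit to a washout period. Making a cut the main rule could drop delayed events due to study aducanumab. This stands, so restricted summaries should be added to the all-data tables and not replace them.

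**Citation of 8.3.** Protocol 8.3 allows withdrawal at the discretion of the investigator or sponsor, so the reference is not empty. The conflict over visits remains, because 8.3 also says: "Participants who are withdrawn from the study are also to return to the site for a FU Visit 18 weeks after receiving their last dose".

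**Conclusion.** The point holds as a gap in the safety reporting. Events after a switch to a commercial disease-modifying drug are counted under the study-treatment group, and nothing in the SAP isolates them. It mainly concerns switches before the February 2024 letter.

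The size is unknown because the documents do not give the number of switchers. The placebo ARIA-E figures of 3.4% to 6.0% rest on assumed switching of 2% to 10% and on full Phase 3 detection of ARIA-E, which the Table 3 MRI schedule makes unlikely. A reader might infer that the ARIA comparison is invalid or that the placebo rate has doubled. The documents do not support that: even the extreme cell leaves a contrast of about 29 points, and no test is planned. The practical relevance lies with rare events, where one case matters.

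Separately, the passages on what happens to a switcher disagree. Protocol 8.1 favours staying in the study. Protocol 8.3 and SAP 3.1 have withdrawn participants return for a follow-up visit. SAP Table 1 footnote 2 calls for withdrawal with no further visits.

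**What to change.** - Keep the all-data AE and ARIA tables as the main presentation.
- In SAP 5.7.1 and 5.7.1.7, add AE and ARIA summaries restricted to events with onset before the first dose of any non-study disease-modifying Alzheimer's drug, with that date derived from the concomitant medication data.
- List events after the switch with the drug named, and report the number of switchers by treatment group.
- In SAP 3.6, state whether the Safety MRI Analysis Set is grouped by actual or randomised treatment.
- For CDR-SB, keep the treatment-policy summary and at most flag post-switch values.
- Reconcile SAP Table 1 footnote 2 with Protocol 8.1 and 8.3 and SAP 3.1 on whether switchers stay in follow-up or return for a follow-up visit.

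The cost is one derived date, a few extra outputs and some SAP wording. No new data are needed, and no follow-up is lost from the main tables.

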5.7.1.1. Common Adverse Events

Table 2 lists the planned analyses of all AEs, most frequently reported AEs, related AEs (related to study drug as assessed by the investigator), and AEs by severity. All analyses will present incidence proportion by treatment group. Where indicated, the analyses will be repeated by treatment group stratified by ApoE status.

Table 2 Planned Analyses of all AEs, most frequent reported AEs, related AEs, and AEs by severity.

Analyses of AE incidence proportion	Repeat stratified by ApoE status?
AEs by SOC/PT by descending frequency	Yes
AEs at least 2% higher in incidence for aducanumab	No
compared to placebo by SOC/PT	
AEs with an incidence of 5% or more by PT	Yes
Severe AEs by SOC/PT	Yes
AEs by maximum severity by SOC/PT	Yes
Related AEs by SOC/PT	Yes

A listing presenting all adverse events will be provided containing the following information: participant number, investigator term, PT with reference ID, onset date, onset study day, end date, end study day, duration of AE (in days), outcome, severity, relation (related to study drug as assessed by the investigator), symptom of ARIA (yes/no), serious (yes/no), study withdrawal (yes/no), concomitant treatment (yes/no), and action on study treatment.

A listing of all adverse events related to amyloid PET ligand, related to tau PET ligand or related to lumbar puncture based on data on adverse event CRF page will be provided.

A listing of non-treatment emergent adverse events will be given too.

5.7.1.2. Deaths

Adverse events with fatal outcome will be summarized by SOC/PT, by treatment group and stratified by ApoE status. A listing of deaths will be provided.

5.7.1.3. Serious Adverse Events

Table 3 lists analyses for incidence proportion for SAEs by treatment group. A listing of SAE will also be provided.

Table 3 Analyses of Incidence Proportion for SAE

Analysis	Repeat stratified by ApoE status?
SAEs by SOC/PT	Yes
Related SAEs by SOC/PT	Yes

5.7.1.4. Other Significant Adverse Events

Analysis of other significant AEs will focus on AEs that lead to a substantial intervention, including premature discontinuation of study treatment and withdrawal from study. Adverse events leading to treatment discontinuation will be summarized by SOC/PT, by treatment group and stratified by ApoE status. The same analyses will be repeated for AEs leading to study withdrawal.

Additional summary will be provided for AEs that lead to drug interruption and drug withdrawal.

A separate summary will be provided for ARIA leading to treatment discontinuation as these were protocol-mandated in some circumstances.

Listings of adverse events that led to discontinuation of study drug and adverse events that led to withdrawal from the study will be provided.

5.7.1.5. Adverse Events of Special Interest

An AE of special interest is an AE of scientific and medical concern specific to this study, for which ongoing monitoring and reporting is required.

Radiographic ARIA (ARIA-E and ARIA-H), as well as any symptoms of ARIA, are considered AEs of special interest and will be entered on the Adverse Event of Special Interest CRF within 72 hours following the receipt of abnormal MRI findings from the central MRI reader.

In order to guarantee uniformity in ARIA reporting, the AE eCRF has a set verbatim term for cases of ARIA. The verbatim terms together with the corresponding MedDRA preferred terms are shown in Table 4.

Table 4 Verbatim Terms and MedDRA Preferred Terms

AESI	Verbatim term	MedDRA preferred term
ARIA-E	Asymptomatic ARIA-E or	Amyloid related imaging
	Symptomatic ARIA-E	abnormality-oedema/effusion

AESI	Verbatim term	MedDRA preferred term
ARIA-H	Asymptomatic ARIA-H	Amyloid related imaging
microhemorrhage	(Microhemorrhage) or	abnormality-microhaemorrhages and
	Symptomatic ARIA-H	haemosiderin deposits
	(Microhemorrhage)	_
ARIA-H	Asymptomatic ARIA-H	Superficial siderosis of the central
superficial	(Superficial Siderosis) or	nervous system
siderosis	Symptomatic ARIA-H (Superficial	
	Siderosis)	
Cerebral	Cerebral Hemorrhage > 1cm	Cerebral hemorrhages > 1cm refers
hemorrhage >		to Intraparenchymal hemorrhages in
1cm		the eCRF, and could be coded to
		various preferred terms, depending
		on type of hemorrhage and location
		of hemorrhage.

Seizures, falls, and hypersensitivity reactions are also considered AEs of special interest.

